#### 7.5.4 Follow-up (visits 4-7)

Patients will be monitored on a 4-weekly basis as shown in the study visit schedule (Table 1), Section 8.2). Patients will be followed up to 16 weeks. If the study is running at the particular site, there is a potential for patients to be recruited into a long term follow up study: CReMSIA (REC ref: 17/EE/0119). Data collection in the CReMSIA study will be recorded in an electronic CRF. Patients will be followed up as per best practice as currently done in the academic centre participating in the trial.

Safety blood tests will be undertaken every 4 weeks. Additional blood tests for monitoring of toxicity/safety of therapy may be undertaken at the physician's discretion. The ACR 50, a validated composite end point, will be used to assess response to therapy as the primary outcome measure. The Health Assessment Questionnaire, EQ-5D-5L and SF-36 will be used to gauge functional ability and improvement in other aspects of the patients' life. The ESS will be used to measure a patient's sleepiness.

Visits 4 - 7 will be carried out every 4 weeks (±7 days) from the baseline visit. The Principal Investigator will need to review any non-compliance with a view to withdrawing patients at their discretion if drug schedule is adversely affected. Patients who consent to the biopsy procedure at Visit 7 (Week 16) will be asked to complete the Pre Biopsy Assessment Form at Visit 7 (week 16) and the Post Biopsy Assessment Form at the safety follow up visit. If the safety

follow-up visit is completed over the phone, this questionnaire will be completed over the phone.

As per normal clinical practice, the GPs of participants with active RA and a cardiovascular risk profile will be informed and asked to review treatment.

All joint assessments from baseline will be performed by a member of the local trial team who will be blinded to treatment allocation. The joint assessor should also complete the VAS physician assessment component of the VAS Pain Score questionnaire. Data will be entered in the electronic CRF by the Investigator or designee who will also coordinate data validation checks and query resolution.

Patients will be asked to complete a patient diary to log when they have taken their medication. The research team should ask patients to return their empty pens in the packaging used to dispense them at each visit. This will be reconciled by the research team against the patient diary and subsequently destroyed by the research team.

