## 8.0 Participant, Study, and Site discontinuation

#### 8.1 Subject Withdrawal from Study/Withdrawal of Consent

Patients who consent to the study but do not undergo synovial biopsy at visit 2 will be withdrawn from the study. Additionally, patients who have a biopsy sample with insufficient RNA for Nanostring analysis will be withdrawn from further participation in the trial. This should be communicated to the patient by the principal investigator or delegated clinician, and patients will receive treatment as per routine care.

Participants may cease randomised treatment and/or be withdrawn from the study if they no longer fulfil the participation criteria, at physician's discretion. Subjects may also withdrawn consent for any reason at any time without prejudice to their normal care or may be withdrawn at any time at the discretion of the investigator for safety, behavioural or administrative reasons. Samples collected prior to withdrawal will be kept unless the patient specifically requests otherwise. The PIS will make clear to participants that data collected prior to withdrawal will be kept and their rights to destroy this data are limited.

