#### 8.2 Withdrawal procedure

At the time of withdrawal, the withdrawal CRF should be completed. The reason for discontinuation should be documented on the applicable CRF and medical records. Patients who discontinue their randomised treatment should be asked to attend the week 16 visit (visit 7) in order to collect data for the primary analysis. However, if the patient discontinues randomised treatment and withdraws consent from attending any further visits, no further study visits should be carried out.

If the patient does not undergo the baseline synovial biopsy, the withdrawal CRF should be completed, and no further study visits should be carried out.

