#### 14.7 Primary endpoint analysis

The primary analysis is within the abatacept arm. It will assess the difference in the change in Clinical Disease Activity Index (CDAI) score at 16 weeks between the biomarker positive and the biomarker negative patients (i.e. Group 1 vs Group 3). This analysis will be on an ITT basis according to original randomisation allocation. The primary outcome will be analysed by analysis of covariance (ANCOVA) with treatment as a factor and baseline value as continuous covariate. If assumptions for ANCOVA are not met, non-parametric ANCOVA will be used. The treatment effect will be reported as least squares mean with 95% confidence intervals.

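### Sections 7.5.4 and 8.1 let investigators end a randomised patient's participation on grounds that section 8.2 does not cover, so week-16 CDAI can be lost avoidably from an ITT primary analysis

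*Protocol*

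**What the plan says.** Four parts of the protocol bear on who is seen at week 16.

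- **Section 7.5.4 (follow-up visits):** the site's lead investigator is to review non-compliance "with a view to withdrawing patients at their discretion if drug schedule is adversely affected". The sentence does not say what the patient is withdrawn from.
- **Section 8.1 (withdrawal):** "Participants may cease randomised treatment and/or be withdrawn from the study if they no longer fulfil the participation criteria". The same section adds that subjects "may be withdrawn at any time at the discretion of the investigator for safety, behavioural or administrative reasons". The first sentence treats stopping treatment and leaving the study as separate outcomes and allows either.
- **Section 8.2 (withdrawal procedure):** "Patients who discontinue their randomised treatment should be asked to attend the week 16 visit (visit 7"), the stated reason being the primary analysis. For these patients, visits end only if they also withdraw consent to attend. Section 7.7 likewise lets patients who stop the intervention keep attending unless they withdraw that consent.
- **Section 14.7 (primary analysis):** "This analysis will be on an ITT basis according to original randomisation allocation". The ITT set in section 14.6 excludes nobody for non-adherence or withdrawal. Section 14.13 imputes missing outcomes by chained equations using the longitudinal data.

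No sentence asks a patient whom the investigator has withdrawn from the study to attend week 16.

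**The concern.** An ITT analysis needs the outcome of every randomised patient as far as it can be obtained. Section 8.2 recognises this for patients who stop treatment. Sections 7.5.4 and 8.1 open another way out, at the investigator's discretion and after randomisation, to which the section 8.2 request does not extend.

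The grounds are also not neutral. Adherence, tolerability and response can all be related to week-16 CDAI, and the trial's hypothesis is that response differs by biomarker status. If withdrawals on these grounds differ between biomarker-positive and biomarker-negative patients on abatacept, the comparison of Group 1 with Group 3 rests more on imputation than it needs to, and could be biased in either direction.

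The ground about entry criteria is a further problem because it cannot sensibly be applied after randomisation, as the working shows.

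**Working it through.** **1. Which patients are asked for week 16.**

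| Situation | Basis | Week-16 visit requested? |
|---|---|---|
| Stops randomised treatment, stays in study | 8.2, 7.7 | Yes, unless consent to visits is withdrawn |
| Withdrawn for non-compliance | 7.5.4 | Unclear: yes if from treatment, not stated if from the study |
| Withdrawn from the study, entry criteria no longer met | 8.1 | Not stated |
| Withdrawn from the study, behavioural or administrative grounds | 8.1 | Not stated |

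The protocol can draw the distinction. For pregnancy, section 12.9 takes the patient off the trial interventions but allows follow-up to continue.

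**2. The entry-criteria ground.** Section 6.1 requires DAS28 above 3.2 and no prior DMARD. All patients receive methotrexate in the trial, so read literally each one stops being DMARD-naive with the first dose. Each patient whose DAS28 falls to 3.2 or below stops meeting the activity criterion. DAS28 and CDAI are recorded every 4 weeks, so this second condition is visible to the site and is close to the outcome itself.

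**3. The plan's sample size, reproduced.** Inputs from section 14.1: difference 10, SD 14.34. Two-sided alpha of 0.05 is assumed, because the protocol does not state it.

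- n per group = 2 × ((1.960 + 1.282) × 14.34 / 10)² = 43.2, so 44. That gives 88 for two groups and 176 for four.
- With 0.842 for 80% power: 32.3, so 33. That gives 66 and 132.
- Inflation for 5% dropout and 5% insufficient RNA: 176 / 0.90 = 195.6, so 196; 132 / 0.90 = 146.7, so 147.

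All the stated figures reproduce.

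**4. Effect of fewer observed patients alone.** Power by two-sample t-test, with outcomes simply missing:

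| Outcome loss | 196 enrolled, 5% RNA failure (186.2 randomised) | 200 randomised |
|---|---|---|
| 5% | 90.0% | 92.0% |
| 10% | 88.4% | 90.5% |
| 15% | 86.5% | 88.8% |

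This cost is small.

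**5. Effect of selective loss (illustration; every rate is assumed).** Let w be the share of a group withdrawn and unobserved, and k the difference in mean CDAI change between those withdrawn and those retained. A complete-case group mean is off by w × k, so the contrast is off by (difference in w) × k.

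- w = 5% and 15%, k = 10: (0.15 − 0.05) × 10 = 1.0 point, or 10% of the design difference.
- Same rates, k = 15: 1.5 points.
- Equal w and equal k in the two groups: 0.

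If a true difference of 10 shrinks to 9, t-test power at 44 per group falls from 89.9% to 82.9%. The opposite pattern would inflate the contrast to 11. The planned analysis imputes, so these are not estimates of its bias.

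**The case against.** **Section 7.5.4 may mean withdrawal from treatment.** Its trigger is the drug schedule, and on that reading section 8.2 already asks for week 16. This stands: a reader might infer that section 7.5.4 removes non-adherent patients from the study, but the text does not say so. The explicit wording is in section 8.1. Section 7.5.4 is ambiguous, and sites could apply it either way.

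**Withdrawn patients are not dropped from the analysis.** They stay in the ITT set and their outcomes are imputed from earlier visits. This also stands. It would be too strong to say that the protocol contradicts or abandons ITT; the conflict is with the data collection that ITT needs. Imputation repairs the loss only as far as earlier visits explain it. Section 14.13 also replaces each missing value with the average of five imputations, which understates uncertainty.

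**Sites are blinded to the biopsy result (7.3) and to treatment (7.4).** This rules out deliberate selection by group. A reader might infer that outcomes will be removed selectively; the documents show only that they can be. Differential loss could arise indirectly, through adherence, tolerability or response.

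**The literal reading of the entry-criteria ground would empty the trial, so no site would use it.** Probably so. It is then loose wording rather than evidence that responders will be excluded. A ground that cannot be applied as written still needs correcting.

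**The losses may already sit within the 5% dropout.** Section 14.1 does not say otherwise, so no claim is made that they add to it.

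**Conclusion.** The point holds as a fault in the follow-up rules. Section 8.1 expressly allows investigator withdrawal from the study, section 7.5.4 leaves the matter open, and the week-16 request in section 8.2 reaches neither case reliably. The protocol therefore permits avoidable, possibly response-related or adherence-related loss of the primary outcome, which weakens the data behind the ITT comparison of Group 1 with Group 3.

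The size of any bias is unknown. The 1.0-point illustration assumes unequal withdrawal (5% v 15%), outcomes 10 points worse in those withdrawn, and a complete-case analysis that is not the planned one. The documents support none of those rates. The effect through numbers alone is minor. The case for acting is that the loss is avoidable and the correction is nearly free.

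**What to change.** Reconcile sections 7.5.4 and 8.1 with section 8.2:

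- State in 7.5.4 and 8.1 that, after randomisation, non-adherence or a change in eligibility status bears on randomised treatment only and does not by itself end study follow-up.
- Extend the week-16 request in 8.2 to all randomised patients, including any whom the investigator withdraws, unless they withdraw consent to further visits.

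Leave the safety ground in 8.1, and all decisions about treatment, as the protocol has them. Nothing here shows them to be wrong.

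The cost is a few wording changes and some additional week-16 visits. The sample size stays at 88 for the primary comparison, 176 over four groups and 196 after inflation.

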#### 7.5.5 Unscheduled visits

While patients will be encouraged to attend for the normal visit schedule, unscheduled visits will be undertaken if the patient is unwell or there are any concerns as to the patient's progress.

#### 7.5.6 Therapy – Methotrexate

All patients will receive oral methotrexate therapy for the duration of the trial in combination with randomised treatment (blinded abatacept or placebo). Patients will be treated with methotrexate as per best practice in line with EULAR recommendations for rheumatoid arthritis. Starting dose should be 15mg per week. This should be escalated to a weekly dose of about 0.3 mg/kg and that this escalation should be done within 4–6 weeks. Optimal therapeutic dose will be around 20–25 mg per week and should be achieved within 4-6 weeks.

#### 7.6 Study Clinical Outcome measures

Patients will be assessed for disease activity using clinical assessments at baseline and 4 weekly thereafter. All patients will be asked to complete a series of case report forms at baseline and during follow-up as per the 3TR-PARTNER-RA Visit Schedule. Patients will be assessed clinically using the ACR 20/50/70, CDAI (Clinical disease activity index), DAS 28, Health assessment questionnaire, the Short Form 36, FACIT-fatigue questionnaire, EQ-5D-5L and the Epworth Sleepiness scale as described below.

#### 7.6.1 ACR Criteria

The 2010 ACR/EULAR Rheumatoid Arthritis classification criteria will be assessed at screening. Patients are scored out of a maximum of 10, based upon the following elements:

- 1. Joint involvement
- 2. Serology positivity of rheumatoid factor (RF) and/or anti-citrullinated protein antibody (ACPA)
- **3.** Acute phase reactants erythrocyte sedimentation rate (ESR) and/or c-reactive protein (CRP)

#### 4. Symptom duration

#### 7.6.2 Diagnosis and Prognosis Evaluation

Following the diagnostic assessments at the screening visits, patients will be diagnosed with Rheumatoid arthritis.

#### 7.6.3 Joint Assessments

The joint assessments will be performed by the delegated blinded joint assessor. The 66/68 joint count which evaluates 66 joints for swelling and 68 joints for tenderness and pain on motion. The hip joints can be assessed for tenderness, but not for swelling. The following joints are included, upper: temporomandibular, sternoclavicular, acromioclavicular, shoulder, elbow, wrist, metacarpophalangeal (MCP), proximal interphalangeal (PIP), and distal interphalangeal; and lower: hip, knee, ankle, tarsus, metatarsophalangeal (MTP), and interphalangeal (IP) joints of the feet.

The 28 joint count will be utilised in order to calculate the DAS28 score, assessing 28 joints for swelling and tenderness in response to pressure or passive motion. The following 28 joints are included: finger proximal interphalangeal joints (8), thumb interphalangeal joint (2), metacarpophalangeal (MCP) (10), wrists (2) (includes carpometacarpal, intercarpal, and radiocarpal), elbows (2), shoulders (2), and knees (2).

Joint pain with palpation or pain on passive motion (either is sufficient) will be scored as:

0 = No pain

1 = Pain

Joint swelling will be scored as:

0 = No swelling

1 =Swelling

Any joints unable to be assessed should be documented.

## 7.6.4 Disease Activity Score (DAS28) and Clinical Disease Activity Index (CDAI)

The components of the DAS28 are the number of tender joints (28 joint count, **TEN28**), the number of swollen joints (28 joint count, **SW28**), the Patient Global Health Index Score (100 mm VAS, **GH**), and the CRP (in mg/L) for DAS28 (CRP) or ESR (in mm/hr) for DAS28 (ESR).

The formulae for determining the DAS28 are as follows:

DAS28 (CRP) =  $0.56*\sqrt{(TJC28)} + 0.28*\sqrt{(SJC28)} + 0.36*\ln(CRP+1) + 0.014*GH(VAS) + 0.96$ 

DAS28 (ESR) = 0.56\*√(TJC28) + 0.28\*√(SJC28) + 0.7\*ln(ESR) + 0.014\*GH

DAS28 values >5.1 correspond to a high disease activity; values between 3.2 and 5.1 indicate moderate disease activity; values between 2.6 and 3.2 define low disease activity, and values < 2.6 represent remission.

Clinical response will be assessed according to the EULAR response criteria as summarised by the table below.

	DAS28 Improvement		
	> 1.2	> 0.6 and ≤ 1.2	≤ 0.6
≤ 3.2	Good response	Moderate response	No response

	> 3.2 and ≤ 5.1	Moderate response	Moderate response	No response
Present DAS28	> 5.1	Moderate response	No response	No response

The components of the CDAI (Clinical disease activity Index) are tender joints (28-joint count), the number of swollen joints (28-joint count), a Patient global health index (10 cm VAS) and physician global health index (10 cm VAS). This provides an assessment of RA disease activity on a scale from 0-76.

CDAI scores:

- High disease activity: >22
- Moderate disease activity:  $10 < CDAI \le 22$
- Low disease activity  $2.8 < CDAI \le 10$
- Remission  $\leq 2.8$

#### 7.6.5 Visual Analogue Scoring – VAS

Participants will be asked to complete three visual analogue scores (VAS), with questions relating to tiredness levels, pain levels, and a patient global health index. The blinded joint assessor will complete the physician global health index score. All VAS scales should be completed by transecting the line, on a 100-mm scale. The scores will be measured in mm.

The pain scale is designed to obtain data relative to the presence or absence of arthritisrelated pain and its severity. The objective is to obtain information from patients on how their pain is on the day of the visit, even though pain may be reported to vary over the course of a day or from day to day.

#### 7.6.6 Health Assessment Questionnaire (HAQ) - Disability Index

The Health Assessment Questionnaire (HAQ) is widely used throughout the world and has become a mandated outcome measure for clinical trials in rheumatoid. The Disability Index is sensitive to change and is a good predictor of future disability and costs.

The HAQ is usually self-administered but can also be given face-to-face in a clinical setting. The Disability Index consists of eight categories assessed by the Disability Index are 1) dressing and grooming, 2) arising, 3) eating, 4) walking, 5) hygiene, 6) reach, 7) grip, and 8) common daily activities. For each of these categories, patients report the amount of difficulty they have in performing two or three specific activities. Patients usually find the HAQ Disability Index entirely self-explanatory.

#### 7.6.7 The Short Form (36) Health Survey- SF-36

The Short Form (36) Health Survey is a survey of patient health. The SF-36 is a measure of health status and is commonly used in health economics as a variable in the quality-adjusted life year calculation to determine the cost-effectiveness of a health treatment. The SF-36 consists of eight scaled scores, which are the weighted sums of the questions in their section. Each scale is directly transformed into a 0-100 scale on the assumption that each question carries equal weight.

The eight sections are: vitality, physical functioning, bodily pain, general health perceptions, physical role functioning, emotional role functioning, social role functioning and mental health.

#### 7.6.8 FACIT-fatigue

The FACIT-Fatigue scale is a 13-item, symptom-specific subscale of the FACIT scales. Lower values of the FACIT-Fatigue score denote higher fatigue (score range, 0 to 52). Cella et. al. validated a brief measure of fatigue in rheumatoid arthritis (RA), the Functional Assessment of Chronic Illness Therapy (FACIT) Fatigue Scale. The FACIT Fatigue was tested along with measures previously validated in RA: the Multidimensional Assessment of Fatigue (MAF) and Medical Outcomes Study Short-Form 36 (SF-36) Vitality. The FACIT Fatigue showed good internal consistency (alpha = 0.86 to 0.87), strong association with SF-36 Vitality (r = 0.73 to 0.84) and MAF (r = -0.84 to -0.88), and the ability to differentiate patients according to clinical change using the American College of Rheumatology (ACR) response criteria (ACR 20/50/70). This suggests that the FACIT Fatigue is a brief, valid measure for monitoring this important symptom and its effects on patients with RA.

#### 7.6.9 Epworth Sleepiness Scale (ESS)

The Epworth Sleepiness Scale (ESS) is a questionnaire developed to assess "daytime sleepiness." The questionnaire consists of 8 questions. Respondents are asked to rate, on a 4-point scale (0-3), their usual chances of dozing off or falling asleep while engaged in eight different activities. The ESS score (the sim of 8 item scores, 0-3) can range from 0-24. The higher the ESS score, the higher that person's average sleep propensity in daily life (ASP), or their 'daytime sleepiness.

#### 7.6.10 EQ-5D-5L

The EQ-5D-5L consists of 2 pages: the EQ-5D descriptive system and the EQ visual analogue scale (EQ VAS).

The descriptive system comprises five dimensions: mobility, self-care, usual activities, pain/discomfort and anxiety/depression. Each dimension has 5 levels: no problems, slight problems, moderate problems, severe problems and extreme problems. The patient is asked to indicate his/her health state by ticking the box next to the most appropriate statement in each of the five dimensions. This decision results in a 1-digit number that expresses the level selected for that dimension. The digits for the five dimensions can be combined into a 5-digit number that describes the patient's health state.

The EQ VAS records the patient's self-rated health on a vertical visual analogue scale, where the endpoints are labelled 'The best health you can imagine' and 'The worst health you can imagine'. The VAS can be used as a quantitative measure of health outcomes that reflect the patient's own judgement.

#### 7.6.11 ACR20/50/70

ACR response will utilise 66/68 joint count which evaluates 66 joints for swelling and 68 joints for tenderness and pain on motion. The hip joints can be assessed for tenderness, but not for swelling. The following joints are included, upper: temporomandibular, sternoclavicular, acromioclavicular, shoulder, elbow, wrist, metacarpophalangeal (MCP), proximalinterphalangeal (PIP), and distal interphalangeal; and lower: hip, knee, ankle, tarsus, metatarsophalangeal (MTP), and interphalangeal (IP) joints of the feet.

ACR20/50/70 response can be used to identify responders/non-responders. The following definition of a responder is used for ACR50:  $\geq$ 50% improvement in tender and swollen joint counts and  $\geq$ 50% improvement in 3 of the 5 remaining ACR-core set measures: patient and physician global assessments (both 10 cm VAS), pain (VAS), disability as measured by HAQ,

and an acute-phase reactant. The same definition is used for ACR20 and ACR70 using  $\geq$ 20% and  $\geq$ 70% improvements respectively.

The ACR20/50/70 will be calculated by the statistician as part of the exploratory analyses.

